8.2.3. Pharmacokinetics from Skin biopsy

The PK analysis of the skin biopsy was from Group A in the study. Since no subjects were randomised in this group, there were no skin biopsies for the PK analysis and therefore no outputs will be generated.

8.3. Pharmacodynamic and Biomarker Analyses

8.3.1. Overview of Planned Pharmacodynamic and Biomarker Analyses

The pharmacodynamic analyses will be based on the Safety population, unless otherwise specified and will be based on Group B subjects only.

The transcriptomic data handling, qc and normalisation will be performed by, or under the direct auspices of Target Sciences (TSci) Statistics, GlaxoSmithKline.

Table 9 provides an overview of the planned pharmacodynamic and Biomarker analyses, with full details of data displays being presented in [Appendix 8: List of Data Displays](#).

Table 9 Overview of Planned Pharmacodynamic and Biomarker Analyses

Endpoint	Absolute				Fold change		
	Summary		Individual		Stats Analysis		
	T	F	F	L	T	F	L
IFN mRNA signature in skin biopsies ²	Y ¹		Y ¹	Y	Y	Y	Y

NOTES :

- T = Table, F = Figure, L = Listing, Y = Yes display generated.
- Stats Analysis = Represents TFL related to any formal statistical analyses (i.e. modelling) conducted.
- Summary = Represents TFL related to any summaries (descriptive statistics) of the observed raw data.
- Individual = Represents FL related to any displays of individual subject observed raw data.
- [1]: By Disease Characteristics (Chronic CLE, Acute CLE, Sub-acute CLE, LET and All).
- [2]: List of genes and probesets are given in Section [11.3.5](#)

RNA will be extracted and hybridised using a balanced batch design. An appropriate microarray platform will be determined at the time of hybridisation, to allow for improvements in technology. The quality of the data will be assessed and then normalised using appropriate methodologies and software.

Microarray mRNA data will be normalised using gcRMA or RMA in Array Studio v5.0 or later. After normalisation, the data will be quality assessed and any samples deemed as QC fails will be excluded from any further analysis. This quality assessment will involve looking for outlying signals in both the normalised expression data and the MAS5 QC metrics generated from each sample. If any samples are excluded, the remaining data will be re-normalised. The output from the normalisation will be \log_2 transformed mRNA intensity data (measured in arbitrary units).

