## Overall Design

This is a double blind (sponsor unblinded) Phase Ib two group study to investigate repeat doses of GSK2646264, a spleen tyrosine kinase (SYK) inhibitor administered via topical delivery, on safety, pharmacodynamic effect and clinical efficacy in active CLE lesions and in acute CLE like lesions induced by an established protocol of PV. The study population will be adult subjects (at least 18 years of age) that have been diagnosed with either subacute or chronic CLE.

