### **9.2. Sample Size Considerations**

There are no formal calculations of power or sample size for this study. The sample sizes have been chosen based on feasibility, to primarily allow the assessment of safety and tolerability of GSK2646264 in patients with CLE.

[figure not shown]
We will recruit approximately 25 patients with CLE into the study with the aim to randomise approximately 20 patients. Approximately 10 patients will undergo PV in group A. PV response rates are estimated at 50% and we expect up to 5 PV positive patients to be randomised into the study. We aim to randomise approximately 15 patients into group B of the study. All patients will be treated with both GSK2646264 and placebo on separate lesions (see Section 6.1 for details).

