Each single/dual stain is assessed at 20x magnification across the whole 1 layer (3.5um slice) of the biopsy by automated image analysis and normalised by area (mm²). The regions of interest are the epidermis, dermis and glass, however only cells within the epidermis and dermis are analysed, which are classified by the automated image analysis software HALO. A manual QC process will be conducted on the software assigned regions of interest if necessary at the discretion of the operator, including but not limited to removal or addition of incorrectly classified areas within HALO. Other artefacts (tissue folding, stain precipitation) will be excluded from the ROI manually at the discretion of the operator and confirmation by the pathologist.

The number of positive cells for each marker will be calculated from the single or dual stain where appropriate. The reportables will include but are not limited to the total number of cells for each marker normalised by area (mm²), total area (mm²), total number of cells per mm², percentage of dual positive cells from total cells and percentage of each marker that is positive for both markers in the dual stains where applicable. These values will be provided for both dermis and epidermis separately, and combined, and will be derived by the BIB group within GSK prior to data transfer.

Histopathology score

- The component scores (patient's parakeratosis, ballooning\hydropic degeneration, epidermal cell-death, junctional inflammation and dermal inflammation scores) are scored twice by two independent investigators. Derivation,

$$\text{Mean component score} = (\text{score 1} + \text{score 2})/2$$

will be used to derive the mean component scores for each patient. This will be used for the

descriptive summaries. If one of the scores missing then the other score will be used as the mean component score.

- Overall histopathology score will be derived by summing derived mean component scores for patient's parakeratosis, ballooning\hydropic degeneration, epidermal cell-death, junctional inflammation and dermal inflammation scores. This will be used for the descriptive summaries.
- Note for listing only: For each score, the overall histopathology score will be derived by summing component scores for patient's parakeratosis, ballooning\hydropic degeneration, epidermal cell-death, junctional inflammation and dermal inflammation scores. This will be used for the descriptive summaries.

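### Array exclusions for the IFN mRNA endpoint rest on an open-ended outlier search by sponsor staff, with no cut-offs, no specified masking and no all-samples run

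*SAP*

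**What the plan says.** SAP 8.3.1 assigns the work to a sponsor group: "The transcriptomic data handling, qc and normalisation will be performed by, or under the direct auspices of Target Sciences (TSci) Statistics, GlaxoSmithKline". The steps are:

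- Normalisation: "Microarray mRNA data will be normalised using gcRMA or RMA in Array Studio v5.0 or later". No rule for choosing between the two methods is given.
- Screening: "This quality assessment will involve looking for outlying signals in both the normalised expression data and the MAS5 QC metrics generated from each sample". No metric list, numeric limit or cap on the number of failures follows.
- Consequence: "any samples deemed as QC fails will be excluded from any further analysis".
- Afterwards: "If any samples are excluded, the remaining data will be re-normalised". No analysis with the excluded samples restored is planned.

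SAP 8.3.2 then fits a mixed model to each probe set with log2 intensity as the response and reports the active-placebo fold change with a 95% interval. SAP 11.4.2 rules out imputation for missing mRNA values, so an excluded array is simply lost.

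On blinding, the protocol synopsis (Overall Design) states: "This is a double blind (sponsor unblinded) Phase Ib two group study". SAP 3.1 puts distribution of the randomisation codes before the final analyses but does not say whether array QC comes before or after that step. On size, protocol 9.2 states: "We aim to randomise approximately 15 patients into group B of the study".

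For the immunohistochemistry images, SAP 11.3.5 allows manual correction of the software-assigned regions at the operator's discretion, "including but not limited to removal or addition of incorrectly classified areas within HALO".

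**The concern.** The screen reads the same normalised values that are later modelled as the outcome, and the decision to fail an array is a judgement. If the person judging knows, or can work out, which lesion and visit an array comes from, arrays that do not fit can be lost more readily on one side of the comparison. The reported interval would not show this, because it treats the retained arrays as if they were all that had been planned.

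It matters more here for two reasons. IFN mRNA is the only efficacy or pharmacodynamic endpoint for which the SAP sets out a full model: SAP 2.1 and 8.1.2 drop modelling of RCLASI because of small numbers, and Table 10 plans only summaries, plots and listings for the exploratory markers. And with about 15 pairs or fewer, two or three arrays carry visible weight.

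**Working it through.** The plan gives no figure for this step, so there is none to reproduce. The check asks how far a few exclusions could move the active-placebo difference.

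**Inputs**
- Pairs: 15 (protocol 9.2, planned). The SAP does not give the number randomised, so 12 and 8 are shown as well.
- Within-patient correlation: an assumption. The precision tables deleted by Amendment 3, kept in protocol 12.6.1, set the within-subject SD at about 0.65 of the tabulated SD (for example 0.28/0.43 = 0.65). Treating the tabulated SD as the total SD, the correlation is 1 − 0.65² = 0.58.
- Interval: two-sided 95%, as in SAP 8.3.2. No true drug effect.

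**Model.** Day 28 value = treatment mean + patient effect + residual. A random-intercept generalised least squares fit with known variances was used, with 40,000 simulated trials per setting. This simplifies the SAP model, which also uses the baseline samples. With all arrays kept, SE of the difference = within-SD × √(2/15) = 0.365 within-SD.

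**Worst case: the highest active Day 28 arrays are removed and their placebo partners kept**

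| Pairs | Arrays lost | Mean shift (within-SD) | 95% interval excludes zero |
|---|---|---|---|
| 15 | 0 | 0.00 | 5.0% |
| 15 | 1 | 0.13 | 6.2% |
| 15 | 2 | 0.24 | 8.8% |
| 15 | 3 | 0.34 | 12.6% |
| 12 | 1 / 2 / 3 | 0.15 / 0.28 / 0.40 | 6.1% / 9.0% / 13.0% |
| 8 | 1 / 2 / 3 | 0.21 / 0.39 / 0.57 | 6.4% / 9.7% / 13.5% |

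**Hand check of one array at 15 pairs.** 0.127/0.365 = 0.35 SE. Then Φ(−1.96 + 0.35) + Φ(−1.96 − 0.35) = 0.054 + 0.010 = 0.064, against 0.062 simulated. A cruder version with independent samples agrees: the highest of 15 standard normals averages 1.74, dropping it moves the mean by 1.74/14 = 0.124 SD, and 0.124/0.365 = 0.34 SE.

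**On the fold-change scale.** The deleted tables give within-SDs from 0.08 to 0.98 log2, used here only for scale. Losing three arrays shifts the difference by 0.335 × 0.08 = 0.03 to 0.335 × 0.98 = 0.33 log2. The spurious active/placebo ratio is then 2^−0.03 = 0.98 to 2^−0.33 = 0.80.

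**Exclusion without labels, 15 pairs**
- The 1, 2 or 3 most extreme arrays dropped from both treatments pooled: mean bias 0.00; interval excludes zero in 4.3%, 3.5%, 3.0%. The variances are held known, so this version cannot show an interval narrowing after trimming.
- The 1, 2 or 3 most extreme active-placebo differences dropped and the SD re-estimated (paired t): mean bias 0.00, but 12%, 19%, 24%.
- Pairs dropped for reasons unrelated to the values: 5%.

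Masking therefore removes the directional bias. Selecting on the outcome can still make the interval too narrow, so preset technical criteria are needed as well.

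**The case against.** The case against is substantial, and much of it stands.

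- **Knowledge of treatment.** A reader might infer that the QC staff know the allocation. The documents do not say so. The sponsor-unblinded label does not name this group, protocol 9.3.2 allows unblinded reviews by managers or study team members for portfolio and budget decisions, and SAP 3.1 controls release of the codes. The supported statement is that masking is not specified.
- **Loss of true responders.** A reader might infer that a strong drug response would be discarded as an outlier. QC works on whole arrays and also uses the MAS5 metrics. Each array carries thousands of transcripts (protocol 7.6.1), while the listed endpoint covers 17 genes. An array that is outlying overall is not the same as a patient with a marked interferon response.
- **Size.** The worst case needs label-aware selection, and one directed array moves the error rate only from 5% to about 6%. Removing whole pairs gives larger figures (9%, 18%, 29%), but the SAP's mixed model can keep the partner sample.
- **Normalisation.** Leaving two methods open adds a choice, but its effect on the active-placebo contrast cannot be computed from the documents.
- **Images.** Classification is automated, manual editing is only if necessary, artefact removal needs a pathologist's confirmation, and these markers are exploratory and planned as descriptive.
- **Existing safeguards.** There is a balanced batch design, a listing of expression by sample, individual plots, and a commitment in SAP 11.4.2 to report excluded subjects with reasons.

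What remains is that SAP 8.3.1 names expression outliers as a ground for exclusion and leaves the judgement open. The reporting commitment is worded for subjects, not arrays. The listing may reveal a gap but does not prevent one.

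**Conclusion.** The concern holds as an avoidable risk of bias, not as a demonstrated bias. Whole arrays may be excluded on an open judgement that includes the normalised expression values, with no cut-offs, no specified masking, no single normalisation and no all-samples analysis, by a group within a sponsor that is unblinded by design.

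The upper end of the risk is the 15-pair result above: about 6%, 9% or 13% instead of 5% for one, two or three directed losses. These rates assume no true effect, correlation 0.58, known variances and Day 28 data only. They describe deliberate or unconscious selection by treatment and are not a forecast.

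The comparison is secondary, labelled exploratory in SAP 2.4, and has no alpha or power attached. The primary safety objective is untouched. The point deserves correction because the remedy is nearly free, but it does not threaten the trial's main purpose.

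**What to change.** Amend SAP 8.3.1, with matching lines in 11.3.5 and 11.4.2:

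1. Carry out array QC, and any manual HALO region editing, on files with treatment, lesion and visit codes removed.
2. State whole-array technical failure criteria with numeric cut-offs in advance, and bar exclusion based on the endpoint probe sets.
3. Name one normalisation method before the data are seen. Either would do; the documents give no ground for preferring one.
4. Lock the list of excluded arrays, with reasons, before the codes are merged, and publish it in the study report at array level.
5. Rerun the active-placebo mRNA model once with all hybridised samples as a sensitivity analysis.

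Barring every expression-based check would go further than needed: a preset whole-array criterion is acceptable if it is applied without labels and does not use the endpoint probe sets. The cost is SAP wording, recoded file names and one extra model run. The drawback is that the sensitivity run may include a noisy array, so it should be read beside the main result and not in place of it.

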8.3.2. Planned Pharmacodynamic and Biomarker Statistical Analyses

Planned Statistical Analyses
Endpoint(s)

 • IFN mRNA signatures
Model Specification
Microarray mRNA data have been collected from the skin biopsy in both GSK2646264 and placebo

Planned Statistical Analyses

treated lesions on Day -5 to -3 (Baseline) and Day 28.

To compare the expression value for each probe set, the following mixed- effects model will be fitted to each probe set, with mRNA intensity (\log_2 scale) as the response variable.

Baseline is defined as the measurement taken pre-dose at baseline of each treated lesions (i.e lesion-specific baseline).

The baseline observation will be defined as an additional response measured on the same subject prior to application of the treatment. Then this observation is not affected by any of the effects included in the basic model for the response.

Visit	Trt	XTrt
Baseline	GSK2646264	NA
Baseline	Placebo	NA
Day 28	GSK2646264	GSK2646264
Day 28	Placebo	Placebo

The model will include:

- Fixed terms: Treatment (Xtrt: Placebo, GSK2646264, NA), Visit, Visit and Treatment (Xtrt) interaction
- Random: Subject (in sas Random intercept /subject=subjid)
- Repeated: Visit (in SAS Repeated visit / subject=subjid type=un)

For each probe set analysed adjusted means with corresponding 95% CI and fold changes with corresponding 95% CI's will be outputted. The fold change is derived from the ratio of the back-transformed estimate of the difference (GSK2646264 – Placebo) between adjusted means.

Since the data will be \log_2 transformed prior to the analysis the treatment effects will be expressed as ratios after back transformation. These ratios can be converted from treatment ratios to fold change values as follows:

- If ratio ≥ 1 then fold change = ratio
- If ratio < 1 then fold change = $-1/ratio$

Model Checking

- Refer to [Appendix 6](#) : Model Checking and Diagnostics for Statistical Analyses.

Model Results Presentation

- Back transformed baseline-adjusted means along with 95% CIs will be calculated for each treatment group. Additionally, fold changes between active and placebo in change from

Planned Statistical Analyses
baseline intensity will be calculated, along with 95% CI.
Endpoint(s)

 IFN mRNA signatures
Model Specification

Microarray mRNA data have been collected from the skin biopsy in from different lesions on Day -5 to -3 (Baseline) and Day 28.
 
To compare the expression value for each probe set, the following mixed- effects model will be fitted to each probe set, with mRNA intensity (log2 scale) as the response variable.
 
The model will include:
 
 Fixed terms: Skin Type Random: Subject (in sas Random intercept /subject=subjid) 
Notes Group B: Skin type refers to uninvolved skin, baseline GSK2646264 lesion, baseline Placebo lesion, GSK2646264 lesion at day 28 and Placebo lesion at day 28
 
For each probe set analysed adjusted means with corresponding 95% CI and fold changes with corresponding 95% CI's will be outputted. The fold change is derived from the ratio of the back-transformed estimate of the difference (GSK2646264 – Placebo) between adjusted means.
 
Since the data will be log2 transformed prior to the analysis the lesion effects will be expressed as ratios after back transformation. These ratios can be converted from treatment ratios to fold change values as follows:
 
 If ratio ≥ 1 then fold change = ratio If ratio < 1 then fold change = $-1/\text{ratio}$
Model Checking

 Refer to Appendix 6: Model Checking and Diagnostics for Statistical Analyses.
Model Results Presentation

Back transformed baseline-adjusted means along with 95% CIs will be calculated for each skin type group. Additionally, following fold changes with 95% CI will also be presented:
 
 - GSK2646264 lesion at day 28 – Uninvolved Skin (skin area H) - Placebo lesion at day 28 – Uninvolved Skin (skin area H) - Baseline GSK2646264 lesion – Uninvolved Skin (skin area H) - Baseline Placebo lesion – Uninvolved Skin (skin area H)

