## **Analysis**

All data will be listed and summarised.

Safety data will be presented in tabular and/or graphical format and summarised descriptively according to GSK's Integrated Data Standards Library (IDSL) standards.

Change from baseline in each clinical activity assessment will be analysed by study part; part A will be summarised descriptively and part B will be analysed using a repeated measures mixed model including visit, treatment and lesion position as fixed effects and subject as a random effect. Estimates of the treatment means and differences will be presented with the associated 95% confidence intervals.

Change from baseline in each IFN mRNA signature endpoints will be analysed by study part; part A will be summarised descriptively and part B will be analysed using a mixed model including treatment and lesion position as fixed effects and subject as a random effect. Estimates of the treatment means and differences will be presented with the associated 95% confidence intervals. If the data is not normally distributed a transformation may be applied to the data.

Full details will be provided in the reporting and analysis plan.

In this sponsor-unblinded bilateral design study, 1 or more unblinded data reviews, using all available data to date, may be carried out by senior managers (not involved in the study conduct) and/or study team members (involved in the study conduct) to aid in portfolio and budget decisions. These administrative reviews will have no impact on the ongoing study. Full details will be provided in the reporting and analysis plan prior to the first administrative review.

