## 6.1. Treatment Assignment

Subjects will be assigned to treatment in accordance with the randomisation schedule generated by Clinical Statistics, prior to the start of the study, using validated internal software.

Skin areas A-C in group A are horizontally distributed across the back of the patient. The PV lesions will be labelled A, B, C. Study drug and placebo will be randomly assigned to lesions A and C. Lesion B will not be assigned a treatment and will be used for the baseline skin biopsy. A further area of uninvolved skin (area D) will also be treated with study drug or placebo in a ratio of 4:1. Another area of uninvolved skin (area E) will not be treated with either study drug or placebo and will be used solely to take a baseline biopsy.

Lesion/Skin Area	Type	Biopsy timing	Receives Drug/Placebo
A	PV lesion	Day 28	✓
B	PV lesion	Baseline	
C	PV lesion	Day 28	✓
D	Uninvolved Skin	Day 28	✓
E	Uninvolved Skin	Baseline	

**Figure 1 Approximate anatomical representation of UV lesion induction sites (A-C) and uninvolvled skin (D and E) for Group A**

Group A subjects will be assigned to the following regimens:

	Skin Sites A/C/D	Assignment ratio
Sequence 1	A/P/A	4
Sequence 2	A/P/P	1
Sequence 3	P/A/A	4
Sequence 4	P/A/P	1

P=Placebo, A= GSK2646264 1%

The nurse administering the treatments may be aware whether a patient is assigned to sequences 1/4 or sequences 2/3, however they will remain blinded to treatment.

In group B, at the day -5 to day -3 visit, prior to pre-dose biopsies being taken, the two chosen lesions will be labelled F and G based on size (F >G). The two lesions will be randomly assigned placebo or study drug. An area of uninvolvled skin (area H) will not

be treated with either study drug or placebo and will be used solely to take a biopsy at baseline. These lesions can be on any part of the body (all 3 lesions must be in the same anatomical area), but the subject must consent to be biopsied from the area with the lesions.

Lesion/Skin Area	Skin Type	Biopsy timing	Receives Drug/Placebo
F	Natural lesion	Baseline and Day 28	✓
G	Natural lesion	Baseline and Day 28	✓
H	Uninvolved Skin	Baseline	

Group B subjects will be assigned to one of the following regimens:

	Skin Sites F/ G	Assignment ratio
Sequence 1	A/P	1
Sequence 2	P/A	1

P=Placebo, A= GSK2646264 1%

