#### **9.4.2. Secondary Analyses**

All plasma GSK2646264 concentration data will be graphically represented, descriptively summarised and listed appropriately. Plasma GSK2646264 concentration time data will be analysed using a population pharmacokinetics (PK) model developed previously using data from study 200196 (FTIH of GSK2646264). Population PK parameters (Cmax, AUC(0- $\tau$ ) and terminal phase half life (t1/2) will be reported. Pharmacokinetic data will be presented in graphical and/or tabular form and will be summarized descriptively. All pharmacokinetic data will be stored in the Archives, GlaxoSmithKline Pharmaceuticals, R&D.

Descriptive statistics of both raw and change from baseline, where appropriate, (i.e. n, arithmetic mean, standard deviation, minimum, median and maximum) will be calculated

for erythema, oedema, dyspigmentation (and scaling in existing lesions only) and modified RCLASI and summarized study part. All data will be listed.

Change from baseline in each clinical activity assessment will be analysed for each lesion type using a mixed effects model fitting visit, treatment and lesion location as fixed effects and subject as random. Estimates of the differences between GSK2646264 and placebo will be calculated and appropriate statistical inferences based on these results will be made.

Descriptive statistics of both raw and change from baseline data, where appropriate, (i.e. n, arithmetic mean, standard deviation, minimum, median and maximum) will be calculated for the IFN mRNA endpoints and summarized by lesion type (PV and natural lesions). All data will be listed.

If data permits, formal statistical analyses of the IFN mRNA endpoints may be conducted.

Change from baseline in each IFN mRNA signature endpoints will be analyzed by study part using a mixed model including treatment and lesion number as fixed effects and subject as a random effect. Estimates of the treatment means and differences will be presented with the associated 95% confidence intervals. Distributional assumptions underlying the analyses will be assessed as appropriate. If these assumptions are strongly violated, appropriate transformations will be investigated and if required alternative statistical analyses considered.

Full details will be provided in the RAP.

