Secondary Analyses	
 All plasma GSK2646264 concentration data will be graphically represented, descriptively summarised and listed appropriately. Plasma GSK2646264 concentration time data will be analysed using a Non-compartmental Analysis (NCA), if data permit. Pharmacokinetic data will be presented in graphical and/or tabular form and will be summarized descriptively. Descriptive statistics of both raw and change from baseline, where appropriate will be calculated for erythema, oedema, dyspigmentation (and scaling in existing lesions only) and modified RCLASI. Change from baseline in each clinical activity assessment will be analysed using a repeated measures mixed effects model with subject random effect and treatment and baseline activity score as the fixed effect. IFN mRNA data will be normalised, back transformed and log2 transformed mRNA intensity data in each IFN mRNA signature endpoints will be analysed using a mixed model with subject random effect and treatment and baseline intensity as the fixed effect. Fold changes will be derived from the back-transformed estimate of the difference between adjusted means.
Exploratory Analyses	
 Descriptive statistics of both raw and change from baseline will be calculated for exploratory Pharmacodynamic/Biomarker endpoints. Change from baseline in these endpoints may be analysed using a mixed model with subject random effect and treatment and baseline activity score as the fixed effect. If data permits, endpoints may be analysed using a mixed model with subject random effect and skin type as the fixed effect to study the difference due to skin type.

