2. SUMMARY OF KEY PROTOCOL INFORMATION

2.1. Changes to the Protocol Defined Statistical Analysis Plan

The following changes were made to the originally planned statistical analysis specified in the protocol amendment 3 [(Dated: 14/DEC/2017)]:

- The secondary endpoint for the plasma concentration of GSK2646264 is clarified in the RAP:

Secondary Objectives	Secondary Endpoints

 • To evaluate the plasma concentrations of GSK2646264 in patients with CLE 	
 • PK parameters, including but not limited to AUC, Cmax, tmax, half-life ($t_{1/2}$) if data permits.

Since no subjects were randomised into Group A, no outputs will be generated for this part. Listings will be produced for the enrolled (PV failure) subjects in Group A who were not randomised.

[figure not shown]
In the protocol Section 9.4.2, it states that 'Change from baseline in each clinical activity assessment will be analysed for each lesions type'. Due to the small number of patients in the study, no formal statistical analysis will be conducted for the RCLASI scores. Descriptive summary for raw and change baseline scores will be calculated and presented.

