8.1.2. Planned Efficacy Statistical Analyses

Due to the small number of patients in the study, no formal statistical analysis will be conducted.

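### The IFN mRNA drug-versus-placebo model in SAP 8.3.2 cannot be fitted because its covariance ignores the lesion; the SAP synopsis gives another model, and the protocol's lesion term is dropped without being listed as a change

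*SAP*

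**What the plan says.** SAP 8.3.2 models log2 mRNA intensity for each probe set. Baseline is treated as an extra response, and the section's layout table has two baseline rows (drug lesion, placebo lesion) and two Day 28 rows. The fixed terms are Xtrt, visit and their interaction. The covariance is a random intercept per subject plus "Repeated: Visit (in SAS Repeated visit / subject=subjid type=un". The same section says: "Baseline is defined as the measurement taken pre-dose at baseline of each treated lesions (i.e lesion-specific baseline".

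The SAP synopsis (section 1, Secondary Analyses) describes the analysis of the same endpoint as a "mixed model with subject random effect and treatment and baseline intensity as the fixed effect". Baseline is there a covariate, with no visit term and no repeated structure.

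The protocol analyses change from baseline. Its synopsis has a "mixed model including treatment and lesion position as fixed effects and subject as a random effect"; section 9.4.2 says "using a mixed model including treatment and lesion number as fixed effects and subject as a random effect". Neither lesion term is defined further. For Group B the only lesion label is the one in Protocol 6.1: "the two chosen lesions will be labelled F and G based on size".

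SAP 2.1 opens with "The following changes were made to the originally planned statistical analysis specified in the protocol amendment 3" and then covers the PK endpoint, Group A and RCLASI. It says nothing about the IFN mRNA model. Protocol 9.4 commits the sponsor to documenting deviations from the protocol analysis in the SAP.

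**The concern.** The REPEATED line identifies an observation only by visit within subject, but each patient has two observations per visit. The model therefore treats two different biopsies as the same measurement. It also contains no term that ties a lesion's Day 28 value to its own baseline, although the section defines a lesion-specific baseline.

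For RCLASI, SAP 8.1.2 says: "Due to the small number of patients in the study, no formal statistical analysis will be conducted". SAP Table 10 plans only summaries and individual displays for the exploratory markers. The IFN mRNA model is thus the one whose planned output (Table 5.2) is a formal comparison of drug with placebo. If it cannot run, someone must choose another. The SAP points in two directions on what that should be, and the study is sponsor-unblinded, so a late choice could be made with results in view.

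**Working it through.** The documents give no power, sample-size or precision figure in current text for this endpoint, so there is nothing to reproduce. The check is algebra on the stated model, then arithmetic on the possible repairs.

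**1. The model as written.** Let g be the subject variance and a, b, c the baseline variance, the covariance and the Day 28 variance of the 2×2 unstructured matrix. For rows (F baseline, G baseline, F Day 28, G Day 28):

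- rows 1 and 2 of V are both (a+g, a+g, b+g, b+g);
- rows 3 and 4 of V are both (b+g, b+g, c+g, c+g).

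Two pairs of identical rows mean rank 2 at most, whatever the values. The Day 28 contrast has variance (c+g) + (c+g) − 2(c+g) = 0. In 10,000 random parameter draws the rank was 2 of 4 every time. With a small ridge added to V, and data simulated for 15 patients, the minimised −2 log-likelihood rose from 225 (ridge 0.1) to 25,441 (0.001) to 2,560,701 (0.00001): it diverges. In addition, g can be absorbed into a, b and c, so only 3 of the 4 covariance parameters are identifiable.

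**2. Confirming the cause.** With the unstructured block indexed by lesion within subject, V has rank 4, all four parameters are identifiable, and −2 log-likelihood is finite (61.3 on the same simulated data).

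**3. Why the choice of repair matters.** Assumptions, none from the documents: subject variance 0.4; lesion-level variance σ² = 0.6 at both visits; ρ = correlation between a lesion's baseline and Day 28 values after removing the subject effect. Planned n = 15 (Protocol 9.2).

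- Lesion-indexed: SE = √(2σ²(1−ρ²)/n). At ρ = 0.45 this is √(1.2 × 0.7975/15) = 0.2526.
- REPEATED deleted, subject intercept only: the estimate is the raw Day 28 difference, with true SE √(2σ²/n) = √(1.2/15) = 0.2828. The ratio is 1/√(1−ρ²) = 1.120.
- The intercept-only fit also under-reports its SE. Its residual pools three within-patient contrasts: the baseline lesion difference (variance σ², n df), the Day 28 difference (σ², n−1 df) and the visit contrast (σ²(1−ρ), n−1 df). Its expectation is σ²[1 − ρ(n−1)/(3n−2)], so reported/true SE is about √(1 − 14ρ/43). The mean SE is slightly lower because of the square root.

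| ρ | True SE, intercept-only ÷ lesion-indexed | Reported/true SE, formula | Reported/true SE, simulated | 95% CI coverage, simulated |
|---|---|---|---|---|
| 0.3 | 1.048 | 0.950 | 0.943 | 93.8% |
| 0.45 | 1.120 | 0.924 | 0.916 | 93.1% |
| 0.7 | 1.400 | 0.879 | 0.870 | 91.7% |

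The simulated columns come from 200,000 runs per setting. A separate simulation gave coverage of 93.7%, 93.3% and 91.5%.

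- Synopsis model: over 400 REML fits at ρ = 0.45, the mean reported SE was 0.247, against 0.245 for the lesion-indexed model, and every fit converged. The synopsis model therefore avoids the loss.

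**4. The lesion term.** With lesion baselines modelled and an 8:7 split of the two sequences, the mean SE without and with F/G was 0.255 and 0.247 for an assumed F−G difference of 0.5 log2 units (3% larger), and 0.265 and 0.248 for 1.0 (7% larger).

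**5. Reach.** The table in SAP 11.3.5 lists 30 probe sets. All use this model.

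**The case against.** - *It fails loudly.* True: it cannot produce a wrong fold change unnoticed. The risk lies in which replacement is chosen.
- *It is a clerical slip.* The layout table in SAP 8.3.2 has a Trt column that identifies the lesion within a patient, so it may simply have been left out of the subject= option. That is plausible, but no model term uses the column, and the reader has to guess.
- *The synopsis is stale.* It still describes an RCLASI model that SAP 2.1 and 8.1.2 withdraw. If so, the governing text is the section that cannot run.
- *Appendix 6 allows adjustment.* It does so on the basis of the data and names no fallback. This defect does not depend on the data.
- *A second model in 8.3.2 can be fitted.* The skin-type model is not singular, and its text mentions a drug-minus-placebo difference. Its listed contrasts are all against uninvolved skin, and its subject intercept alone does not use the lesion baselines. Listings 40 and 41 also refer to statistical output for IFN proteins, but SAP Table 10 plans no such analysis.
- *The percentages rest on assumed correlations and on a repair that nobody has proposed.* This stands: they show that repairs differ, not what will happen. A smaller check (600 to 1,000 runs) put intercept-only coverage at 94.5% at ρ = 0.45; the larger runs give 93.1% to 93.3%. At an assumed n of 6, without Kenward-Roger, the lesion-indexed fit itself reported 0.76 of its true SE, against 0.89 for intercept-only. The Kenward-Roger method already in Appendix 6 therefore needs to stay.
- *Omitting F/G is harmless.* Nearly so. Treatment is randomised 1:1 to F and G, so the contrast is not biased and the cost is small. Equating the protocol's lesion term with F/G is an inference. What remains is the unlisted change.

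**Conclusion.** All three parts hold. The covariance in SAP 8.3.2 is singular for every patient with two lesions measured at a visit, which is the Group B design; this needs no assumption. The synopsis and section 8.3.2 give different models for one endpoint. The protocol's lesion term, and the switch of response from change from baseline to log2 intensity, are not among the changes in SAP 2.1.

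The consequence is moderate. This is a secondary endpoint and an exploratory, interval-based comparison in a safety study with no power calculation, and Protocol 9.4.2 makes formal analysis conditional on the data. The repair can be specified without seeing treatment results. It should be named in advance because the obvious shortcut costs 5% to 40% in SE and 1 to 3 points of coverage at n = 15, for assumed ρ between 0.3 and 0.7. The missing F/G term by itself is minor.

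**What to change.** State one model, identically, in the SAP synopsis and section 8.3.2. Either of these works:

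- **Lesion-indexed:** fixed Xtrt; `random intercept / subject=subjid`; `repeated visit / subject=subjid*site type=un`, with site = F or G; Kenward-Roger degrees of freedom.
- **Synopsis version:** Day 28 values, with treatment and the lesion's own baseline as fixed effects and subject as random.

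Restore the lesion term as site F/G, or list and justify its removal in SAP 2.1, together with the change of response. If site goes into the lesion-indexed model, say whether its effect is taken as equal at both visits; site×visit relaxes that. Dropping the redundant visit and visit×Xtrt terms is optional tidying. Test the code on dummy data before the codes are released.

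The cost is SAP wording and a few lines of code, with no new data. Site uses one degree of freedom. Under the assumptions above (ρ = 0.45, n = 15, 8:7 split) the SE is 0.2526 without site, 0.2527 with it and 0.2531 with site×visit.
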